10.4.7 Report of severe adverse events

Upon becoming aware of any severe adverse events (SAE), the investigator should promptly (within 24 hours) report all SAEs in writing to the sponsor and submit follow-up reports.

Upon receipt of safety-related information from any source, the sponsor should conduct an analytical assessment, including severity, association with the experimental drug, and identification of an expected event. The sponsor should report suspicious and unexpected severe adverse reactions (SUSAR) to the investigator, the clinical trial institution and the ethics committee as soon as possible. Meanwhile, the sponsor should report SUSARs to the National Medical Products Administration and the health authorities. For fatal or life-threatening SUSARs, the sponsor should report to the National Medical Products Administration immediately after first being informed and within 7 natural days, and report relevant follow-up information within the following 8 days; for non-fatal or non-life-threatening SUSARs, or information about other potential severe safety risks, the sponsor should report to the National Medical Products Administration immediately after first being informed and within 15 natural days.

10.4.8 Medical management of adverse events

Subjects should be informed to record clinically significant adverse events at any time. Early suspected symptoms of COVID-19 (such as fever, dry cough, fatigue, nasal congestion, rhinorrhoea, pharyngalgia, myalgia, diarrhea, polypnea, and dyspnea), COVID-19 infection, grade 3 or above AEs and SAEs, if any, should be reported, at all times, to the investigator who should conduct investigation, verification and follow-up after being informed, until such events are resolved, and finally complete the detailed case investigation and follow-up records. In case of severe or fatal COVID-19 infection, further thematic investigations are required to determine the presence of ADE/VED. If subjects experience grade 3 or above AEs or SAEs after vaccination, the investigator should provide them with appropriate treatment or medical consultation in a timely manner to alleviate or relieve their suffering. If necessary, the green channel for medical treatment should be initiated to ensure timely medical treatment, and the medical measures and results should be recorded in detail during this process.

Adult female subjects are required to take effective contraceptive measures within 2 weeks before enrollment and 1 month after full-course vaccination. If an unplanned pregnancy occurs in subjects between enrollment and 1 month after full-course vaccination, the investigator should immediately stop vaccination, prematurely terminate all studies, and record it as an AE. The investigator should follow up the health of both subjects and children up to 12 months after birth.

10.5 Immunogenicity and cellular immunity evaluation

10.5.1 Blood sample collection

Blood sample collection schedule, see “8.8 Study Plan”. About 5 ml of venous blood need to be collected from subjects to test the immunogenicity.

10.5.2 Blood sample processing and storage

The venous blood collected for immunogenicity testing needs to be centrifuged and separated in time on the same day. The serum should be divided into 4 tubes with at least 0.5ml in each tube and frozen at -20°C for unified examination. Sera in tube 1 (set A) and tube 2 (set B) are used for antibody testing. Sera in tube 3 (set C) and tube 4 (set D) are available as reserve samples, which will first be kept by the testing team on site, until the immunogenicity test report is issued and verified to be correct. Biological samples collected in this study will be properly stored as required and will be used only for the research tests specified in the protocol. After the use of biological samples, except the remaining serum, the remaining samples will be destroyed by the testing unit in accordance with the relevant provisions. If any additional testing of the remaining serum is required, the approval of the ethics review committee and the subjects' consent must be sought.

10.5.3 Antibody detection

The neutralization antibody should be detected by microcytopathic method. The China National Institutes for Food and Drug Control is entrusted to detect neutralizing antibody concentrations of pseudovirus, and the Chinese Center for Disease Control and Prevention to detect neutralizing antibody concentrations of live viruses. The China National Institute for Food and Drug Control is entrusted to detect IgG antibody by ELISA.

10.5.4 Evaluation indexes and criteria

The positive seroconversion rate of SARS-CoV-2 antibody, GMT (or GMC), and GMI are taken as the evaluation indexes of immunogenicity.

Determination criteria of positive seroconversion of neutralizing antibodies: negative if antibody titer < 1:4; positive if antibody titer \geq 1:4. The antibody positive seroconversion is considered if antibody titer is < 1 : 4 before immunization and \geq 1 : 4 after immunization, or antibody titer is \geq 1:4 before immunization and the antibodies increase by \geq 4 fold increase after immunization.

10.6 Data management

10.6.1 Data collection, recording and reporting

All test data should be recorded in the electronic data collection (EDC) system and made available to the sponsor. Only authorized investigators and researchers are allowed to access the system during the experiment. All data in the EDC system comes from source files. All modifications to source files are underlined above the original section with a signature and date next to the modified content. Any modifications to data in the EDC system will be recorded by the system. Source files include informed consent, original record books, diary cards, contact cards, etc., which should be properly kept by the investigator.

10.6.2 Monitoring of data records

The supervisor should monitor the data records periodically and irregularly until all data entry, verification and cleaning are completed. Data verification by the supervisor mainly refers to consistency verification, namely, to check the consistency between the data in the EDC system and the original records. The data administrator performs logical checks on the data.

10.6.3 Data quality control

A final data verification should be performed after all data entry, verification and cleaning are completed and before the database is locked.

10.6.4 Database lock

Blind verification is required before statistical analysis. Blind verification mainly determines the population to be analyzed according to evaluation criteria, including FAS data set, PPS data set and safety analysis data set under the ITT principle, and determines the violation/deviation of the scheme and its impact on the analysis data set. Blind verification should be performed by the data administrators with the participation of the investigator and the program leader or their representatives. In addition to the above data review, the main investigators, statistical analysts, data administrators and the sponsor should further discuss and confirm the statistical analysis plan based on the main contents of the experimental scheme. After blind verification is confirmed, the database will be locked, and the statistical analysis plan will be determined simultaneously.

10.7 Statistical considerations

10.7.1 Statistical analysis plan

The statisticians are entrusted by the sponsor to undertake the task of statistical analysis and participate in the whole process from experimental design, implementation to analysis and summary. After the experimental scheme is formulated and approved by the ethics committee, the statisticians will write and formulate a statistical analysis plan to define the details of statistical analysis.

10.7.2 Sample size considerations

In the phase II trial:

Assume that the positive seroconversion rate of the vaccine group is 80%, that of the placebo group is 30%, and the ratio between vaccine and placebo is 2:1, while the test level is set to bilateral 0.05, if there're 100 subjects enrolled in the vaccine group and 50 subjects enrolled in the placebo group, the difference between both groups can be determined with 99.99% certainty. Therefore, for each immunization schedule of each age group in the phase II trial, 100 subjects are enrolled in the mid-dose group, 100 in the high-dose group and 50 in the placebo group respectively.

10.7.3 Analysis data set

10.7.3.1 Safety set

Safety set (SS): all subjects who have received at least one dose of the experimental vaccine are included. For those with wrong vaccination number, safety evaluation will be conducted according to the vaccine group actually administered by the subjects following the principle of ASaT (All Subjects as Treated). SS is mainly used for safety evaluation of vaccines.

This experiment will define the SS of each dose separately based on the safety analysis after different doses of vaccination.

10.7.3.2 Immunogenicity evaluation data set

Full analysis set (FAS): all subjects who follow the principle of intention analysis (ITT), have been randomized, have completed at least one dose of vaccination, completed the pre-immunity evaluation of blood sampling, and have valid antibody values are included. The subjects with incorrect vaccine number should be evaluated for immunogenicity according to their primary randomized group.

Per protocol set (PPS): all subjects who have not violated the inclusion/exclusion criteria, have been randomized, have completed the full-course vaccination, completed all the blood collection before and post vaccination for immunogenicity evaluation, and valid antibody values are included. Among them, subjects meeting the following conditions are not allowed to enter PPS:

- 1) Those with severe information and data missing after randomization;
- 2) Those who have seriously violated the protocol;
- 3) Those who have received the wrong inoculation or incorrect dose;
- 4) Those who have received concomitant medications or concomitant vaccines that affect the immunogenicity evaluation.

The corresponding PPS should be defined for each time point of immunogenicity evaluation in the basic immunization stage. FAS and PPS are mainly used to evaluate the immunogenicity of vaccines.

Immune persistence set (IPS): all subjects who have undergone the immune persistence evaluation stage and completed blood sampling at the time point for immune persistence evaluation and have antibody values are included. The immune persistence set should be defined for 3 months, 6 months, and 12 months after vaccination.

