8.8.2 Long-term Safety and Immune Persistence Study

Subjects will be followed up passively during a 12-month long-term safety observation after whole immunization to verify the incidence of serious adverse events during the study period. A visit (face-to-face/telephone visit) will be conducted once each at 3, 6, 9 and 12 months after full-course immunization to collect the data on the incidence of SAEs.

To observe the immune persistence in subjects who have completed the full-course immunization, about 5 ml of venous blood will be collected at 3 months (+30 d), 6 months (+30 d) and 12 months (+30 d) after the full-course immunization, and the serum will be separated for antibody detection and immune persistence evaluation.

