9.4 Exclusion Criteria for Subsequent Vaccinations

After the enrollment, during the study period, if the COVID-19 epidemiological history, suspected COVID-19 clinical manifestations appear, epidemiological investigation and nucleic acid tests shall be carried out immediately, chest CT shall be taken if necessary, and the subjects shall undergo quarantine observation according to local epidemic prevention and control. If the subject is diagnosed with a COVID-19, he/she shall withdraw from the clinical trial, and accept the reasonable treatment from local center for disease control as required.

If one of the following (1) to (3) adverse events (AE) occurs, the vaccination shall be prohibited, other research procedures can be continued according to researchers' discretion; If one of the following (4) to (5) adverse events occurs, it is up to the investigator to determine whether the vaccination shall be continued; If one of the following (6) to (7) adverse events occurs, the vaccination shall be delayed within the time window specified in the protocol.

- (1) Any serious adverse events with cause association with vaccination;
- (2) Serious allergic response or hypersensitivity after the vaccination (including urticaria/rash within 30 minutes after vaccination);
- (3) Any diagnosed or suspected auto-immune diseases or immunodeficiency diseases (including human immunodeficiency virus (HIV) infection).
- (4) Emerging chronic diseases after vaccination or acute attack of chronic diseases;
- (5) Severe intolerable adverse reaction occurs.
- (6) Suffering from acute diseases at vaccination (acute diseases refer to moderate or severe diseases with or without fever);
- (7) Axillary temperature ≥ 37.0 °C at vaccination.

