10.3.3 Concomitant Medications and Concomitant Vaccination

Allowed medications: if the subjects experience AE during the clinical trial, necessary drug treatment is allowed, the name, administration route, reason and medication time shall be recorded.

Allowed vaccination: during the study period, subjects can receive routine immunization according to the product instruction, however, there needs an interval between routine inoculation and the previous dose of the experimental vaccine, it is 7 days for subunit vaccine and non-live vaccine, 14 days for live attenuated vaccine. Emergency vaccination for medical treatment is allowed, for example, rabies or tetanus vaccines can be timely inoculated according to the instructions. The name, usage, time and the vaccination site of concomitant vaccination shall be recorded.

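### The immune persistence set drops the protocol's own exclusion for interfering vaccines, so titres raised by another COVID-19 vaccine would count as persistence of the study vaccine at 3, 6 and 12 months

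*Protocol*

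**What the plan says.** Protocol section 8.7.2 lists seroconversion rates and antibody levels at 3, 6 and 12 months after the full course as a secondary endpoint. Section 8.8.2 gives the purpose of the later blood draws: "To observe the immune persistence in subjects who have completed the full-course immunization".

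Section 10.7.3.2 defines the sets:
- **IPS.** It takes all subjects who entered the persistence stage and meet the closing condition: "completed blood sampling at the time point for immune persistence evaluation and have antibody values are included". The time points are fixed: "The immune persistence set should be defined for 3 months, 6 months, and 12 months after vaccination". No exclusion is listed.
- **PPS.** Condition 4 keeps out "Those who have received concomitant medications or concomitant vaccines that affect the immunogenicity evaluation". Its reach is limited: "The corresponding PPS should be defined for each time point of immunogenicity evaluation in the basic immunization stage".

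Two other sections bear on the point. Section 10.3.3 says that "during the study period, subjects can receive routine immunization according to the product instruction", subject to intervals from the study doses, and also allows emergency vaccination. It requires the name, usage, time and site of any such vaccination to be recorded, and does not mention another COVID-19 vaccine. Section 9.4 deals with diagnosed infection: "If the subject is diagnosed with a COVID-19, he/she shall withdraw from the clinical trial".

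**The concern.** The protocol treats an interfering vaccine as a reason to leave a subject out of the PPS during the short basic immunization stage. It drops that safeguard for the following months, when there is more time for such a vaccination to occur. The IPS is a complete inclusion rule, so an analyst who follows it must keep a 12-month sample from a subject who received another COVID-19 vaccine at, say, month 5.

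That titre does not measure how long the response to the study course lasts, which is what section 8.8.2 sets out to observe. Persistence would be overstated in any vaccine arm so affected, and placebo rates would rise for a reason unrelated to the study vaccine. As long as the same subjects stay in follow-up, the share affected cannot fall from one draw to the next, so the 12-month result is the most exposed.

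**Working it through.** **1. Plan's own figure.** The protocol gives no figure for persistence. Its only power statement (section 10.7.2: 80% vs 30%, 100 vs 50 subjects, two-sided 0.05, 99.99%) concerns seroconversion after the full course. It reproduces at 0.999995 by normal approximation and 0.99998 by Fisher's exact test. It is not at issue.

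**2. Does any rule remove these samples?**

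| Rule | Section | Removes a month 3-12 sample drawn after another COVID-19 vaccine? |
|---|---|---|
| IPS definition | 10.7.3.2 | No: no exclusion listed |
| PPS condition 4 | 10.7.3.2 | No: PPS time points lie in the basic immunization stage |
| Withdrawal on diagnosis | 9.4 | No: concerns infection, not vaccination |
| Concomitant vaccination | 10.3.3 | No: calls for recording, sets no analysis rule |
| Review of deviations before lock | 10.6.4 | Not stated: names FAS, PPS and safety set, not the IPS |

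**3. Size, under assumptions.** The documents give neither the share affected nor the rise, so both are assumed: a share q of an arm is boosted before the draw, and its titres are k times what they would otherwise have been.

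*GMT.* The mean log titre rises by q·log k, so the arm's GMT is multiplied by k^q.

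| | k = 4 | k = 10 |
|---|---|---|
| q = 10% | 4^0.1 = 1.15 | 10^0.1 = 1.26 |
| q = 20% | 4^0.2 = 1.32 | 10^0.2 = 1.58 |

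In a full vaccine arm of 100 (section 8.2), these shares are 10 and 20 subjects.

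*Rate.* Suppose every boosted subject is positive and would otherwise have had the arm's true rate p. The observed rate is then p(1 − q) + q, an increase of (1 − p)q. For an assumed p = 50%:
- q = 10%: 0.50 × 0.90 + 0.10 = 55%
- q = 20%: 0.50 × 0.80 + 0.20 = 60%

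**4. Price of the exclusion.** Setting aside a share q widens a confidence interval for the log GMT by about 1/√(1 − q) at the same standard deviation: 1/√0.9 = 1.05 and 1/√0.8 = 1.12. That is 5% to 12% wider.

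**The case against.** The strongest reply is that handling of intercurrent vaccination for a secondary endpoint is normally settled in the SAP, which section 10.7.1 leaves to define the details and which is not at hand. An all-available-samples set is also a recognised choice. Moreover, section 10.3.3 allows routine and emergency vaccination, and section 4.2 describes competing inactivated COVID-19 vaccines as still in phase III. Receipt of one could therefore be treated as a deviation.

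Part of this stands. An SAP could add the rule, silence in section 10.3.3 is not permission, and the vaccination data needed are already to be recorded. But the IPS is not left open: the protocol states a closed rule, and an SAP that follows it keeps these samples. An all-samples analysis answers a different question from the one in section 8.8.2, and the protocol's own PPS shows that interfering vaccines were judged to matter.

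Three stronger readings are tempting and are not supported:
- **The IPS takes in subjects who did not complete the course.** Section 8.8.2 draws persistence blood from full-course completers and the IPS requires entry to that stage, so at most the wording needs aligning.
- **Placebo recipients learn their arm and seek vaccination elsewhere.** Sections 8.5 and 10.8 describe unblinding by sponsor, investigator and statistician representatives, for analysis. Neither says that participants are told. Unequal uptake between arms is therefore speculation, and no figure is given for it here.
- **Undiagnosed infection should be excluded from the main set.** Such infection may occur, since testing under section 9.4 is triggered by exposure or symptoms. But the product is a whole inactivated virus, and no planned assay is stated to separate infection from vaccination. The only available marker is a rise in titre, and excluding on the outcome would bias the main estimate downward.

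**Conclusion.** The point holds in a limited form. The IPS does not carry forward PPS condition 4, so antibody raised by another COVID-19 vaccine would be reported as persistence of the study vaccine at 3, 6 and 12 months.

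The actual size is unknown. The inflation of 1.15 to 1.58 in an arm's GMT, and of a true 50% rate to 55-60%, rests wholly on the assumed q of 10-20% and k of 4-10; the rates also assume that every boosted subject turns positive. If nobody receives another COVID-19 vaccine, there is no bias from this source. Only a secondary endpoint is affected, so this is a change that should be made and not one that puts the trial's main result in doubt.

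**What to change.** 1. **Main persistence analysis.** In section 10.7.3.2, or in the SAP with a cross-reference, apply PPS condition 4 to the IPS at each of 3, 6 and 12 months. Set aside values drawn after recorded receipt of another COVID-19 vaccine or after confirmed infection. The second part only makes the analysis consistent with withdrawal under section 9.4.
2. **Missing data.** State that values set aside are not replaced under the LOCF rule of section 10.7.6. Carrying an earlier value forward would itself overstate persistence if titres wane.
3. **Sensitivity analyses.** Report the all-samples IPS as now defined. Separately, address possible undiagnosed infection by, for example, setting aside values after a 4-fold or greater rise between consecutive post-course draws. Count from the day-28 draw, so that a rise between days 14 and 28 in the two-dose groups is not mistaken for infection.
4. **Data collection.** Ask for receipt and date of any other COVID-19 vaccine at the 3-, 6-, 9- and 12-month visits, which section 8.8.2 describes as collecting SAEs.
5. **Wording.** Repeat the full-course condition of section 8.8.2 in the IPS definition.

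The cost is a few sentences and one question at existing visits. The main persistence set becomes somewhat smaller, and the exclusions may be informative; comparison with the all-samples analysis shows how much they matter.

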10.7.4 Statistical analysis method

10.7.4.1 General principles

Measurement data are statistically described by the mean, median, standard deviation, maximum value and minimum value; counting data or grade data are described using frequency number and frequency. All statistical analyses are done with statistical software SAS 9.4 or higher version.

10.7.4.2 Subject disposition and demographic information

The number of subjects enrolled in each group, the number of subjects who completed the trial and the number of cases in each analysis set are summarized respectively and the subjects who dropped out and the reasons for dropout are analyzed. The demographic characteristics of subjects in each group are statistically described.

10.7.4.3 Immunogenicity assessment

The positive rate and positive seroconversion rate of the COVID-19 antibody after immunization are calculated respectively, the bilateral 95% confidence interval is calculated by Clopper-Pearson and the differences between groups are statistically tested by chi-square test/Fisher's exact test.

The differences between groups in the COVID-19 antibody GMT of subjects after immunization, the antibody after immunization and its growth compared with that before immunization are statistically tested by analysis of variance after logarithmic transformation using the geometric mean and 95% confidence interval.

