8.7 Clinical endpoints

8.7.1 Primary endpoints

- “the positive seroconversion rate and antibody level of neutralizing antibody against COVID-19 virus 28 days after the whole immunization”
- The positive seroconversion rate of IgG antibody (ELISA method) against COVID-19 virus 28 days after the whole immunization

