8.8 Study plan

8.8.1 Phase II clinical study plan

For each age group, the phase II trial is only permitted, when safety and tolerability have been preliminary confirmed in the phase I trial 7 days after the 1st dose of the high-dose group.

Volunteers will be screened from the resident healthy adults aged 18 years and above in accordance with the principles of voluntary registration, informed consent, and compliance with inclusion and exclusion criteria. When enrolled, every subject will be given a code number and get the correspondingly numbered vaccine shot. Subjects in the 18-59-year-old group will receive the experimental vaccine or placebo according to the 2-dose 0-14 d or 0-28 d immunization schedule, or 3-dose 0-28-56 d immunization schedule, respectively. Subjects in the ≥ 60 -year-old group will receive the experimental vaccine or placebo according to the 3-dose 0-28-56 d immunization schedule. After each dose, the subjects need to stay on site for 30 min to see if there's any immediate response. During the following 7-day systematic follow-up observation, the subjects should record their daily observation results on the Diary Card. After each dose, subjects will receive a telephone visit on day 3 and an intensive visit on day 7 by the researchers, to verify the safety of the vaccination. Subjects should carry out safety observations on their own from days 8-28 after each vaccination. After each dose, subjects will receive a telephone visit on day 14, and an intensive visit on day 28 by the investigator, to verify the safety of the vaccination.

About 5 ml of venous blood will be collected from subjects in the 2-dose immunization group before the 1st dose and 14 and 28 d after whole immunization, and from subjects in the 3-dose immunization group before the 1st and 3rd dose and 28 d after whole immunization, respectively, in order to determine the serum antibody levels. See Tables 2-7 for visit time, time window and visit content for different age groups.

Table 2. Visit content and schedule for 0-28-56 d immunization group

Visit No.	V0	V1	V2	V3	V4	V5	V6	V7	V8	V9	V10	V11	V12	V13
Content	Pre-immune 0-7 d	Day 0	3-5 d after V1	7-8 d after V1	14-21 d after V1	28-35 d after V1	3-5 d after V5	7-8 d after V5	14-21 d after V1 天	28-35 d after V5	3-5 d after V9	7-8 d after V9	14-21 d after V9	28-35 d after V9
1	Informed consent	X												
2	Collection of demographic information	X												
3	IgG, IgM screening	X												

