10.1 The Selection of Subjects

The local healthy volunteers aged ≥ 18 shall be enrolled, and provided with oral and written information of the study, and asked to sign the informed consent form.

After the signing of informed consent, the volunteers were screened according to the inclusion and exclusion criteria, qualified subjects can be registered into the group and assigned research number. Subjects from different age groups will be assigned to the corresponding study number according to the age from young to old.

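### Antibody titre and its growth over baseline are each tested by analysis of variance with no covariate named; one model adjusted for baseline titre and age would give a single answer, at a modest gain in precision

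*Protocol*

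**What the plan says.** **Endpoint.** Section 8.7.1 lists "the positive seroconversion rate and antibody level of neutralizing antibody against COVID-19 virus 28 days after the whole immunization". Growth over baseline is not an endpoint in 8.7.1 or 8.7.2.

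**Indexes.** Section 10.5.4 adds growth: beside the seroconversion rate, "GMT (or GMC), and GMI are taken as the evaluation indexes of immunogenicity". No order is given between GMT and GMI.

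**Test.** Section 10.7.4.3 says that group differences in the post-immunization antibody and "its growth compared with that before immunization are statistically tested by analysis of variance after logarithmic transformation". It names no covariate. Section 10.7.1 leaves analysis details to a statistical analysis plan.

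**Data available.** Section 8.8.1 takes blood in the 2-dose schedules "before the 1st dose and 14 and 28 d after whole immunization", and the 3-dose schedule also has a sample before dose 1 (Tables 3, 5 and 7). The visit tables include "Collection of demographic information". Age is known when numbers are given out (10.1): "Subjects from different age groups will be assigned to the corresponding study number according to the age from young to old". The stated use of these data in 10.7.4.2 is descriptive: "The demographic characteristics of subjects in each group are statistically described".

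**The concern.** Titre and growth answer the same randomised question. If by chance one arm holds more subjects who already have antibody, its post titre is pushed up while its growth tends to be pushed down. The two tests can then fall on different sides of 0.05, and the protocol does not say which one decides.

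Baseline-positive subjects are possible here. The seroconversion rule in 10.5.4 has its own branch for a pre-immunization titre of at least 1:4. An IgG/IgM screen is scheduled in 8.8.1, but no exclusion criterion in 9.3 acts on its result.

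The contrast with most to gain is medium against high dose, where the titre difference may be small. The protocol's only power statement concerns vaccine against placebo seroconversion.

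**Working it through.** **1. The plan's own figure.** Section 10.7.2 states 99.99% power for seroconversion of 80% against 30%, with 100 against 50 subjects, two-sided 0.05.
- Pooled rate: (80 + 15)/150 = 0.6333.
- SE under no difference: √(0.6333 × 0.3667 × 0.03) = 0.0835. SE under the alternative: √(0.16/100 + 0.21/50) = 0.0762.
- z = (0.50 − 1.96 × 0.0835)/0.0762 = 4.42, so power is 99.9995%. Exact Fisher gives 99.998%.

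The figure reproduces. It does not concern titre or growth, for which no power is given.

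**2. One model, one contrast.** If log post = a + τ·arm + b·log baseline, then subtracting log baseline from both sides gives log growth = a + τ·arm + (b − 1)·log baseline. The arm effect τ, its standard error and its p-value are identical, so titre and growth cannot disagree.

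**3. Large-sample precision.** Take equal pre and post variances and correlation ρ. Relative to the titre analysis (1), the variance is 2(1 − ρ) for growth and 1 − ρ² for the adjusted model. The latter is never above 1, and 2(1 − ρ) − (1 − ρ²) = (1 − ρ)² is never negative. For ρ = 0.1, 0.3 and 0.5, growth has 1.80, 1.40 and 1.00, and the adjusted model 0.99, 0.91 and 0.75.

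**4. Cost at these sample sizes.** With k uninformative covariates, variance is multiplied by 1 + k/(df − k − 1).
- 100 against 100 (df 198): +0.5% for k = 1, +1.6% for k = 3.
- 100 against 50 (df 148): +0.7% for k = 1, +2.1% for k = 3.
- Break-even multiple correlation for these cases: about 0.07 to 0.14.

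**5. Age alone.** Assumed: residual SD 0.5 log10, ages uniform over 18-59 (variance 41²/12 = 140), slope 0.006 to 0.010 log10 per year. If every baseline is below 1:4, baseline titre is constant and drops out, leaving age and sex (k = 2, factor 1 + 2/195 = 1.010).
- Slope 0.006: 0.25/(0.25 + 0.0050) × 1.010 = 0.99.
- Slope 0.010: 0.25/(0.25 + 0.0140) × 1.010 = 0.96.

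These match simulated ratios of 0.99 and 0.96 (4000 trials per setting, two arms of 100).

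**6. Some subjects positive at baseline, strong effect.** Same simulation, positives assumed to respond 10-fold higher. Variance ratios:

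| Baseline-positive | Age slope | Adjusted / titre | Adjusted / growth |
|---|---|---|---|
| 3% | 0.006 | 0.91 | 0.99 |
| 5% | 0.006 | 0.88 | 0.99 |
| 5% | 0.010 | 0.84 | 0.95 |

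A ratio of 0.84 is worth 100 × (1/0.84 − 1) = 19 extra subjects per arm of 100; a ratio of 0.99 is worth 1.

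**7. Sensitivity to that effect.** A second simulation used 2000 trials, two arms of 100, GMT ratio 1.5, residual SD 0.5 and adjustment for baseline only. Negatives were set at log10 2 = 0.30, and positives averaged 1.2 log10. A slope of 0.5 or 1 on log baseline means that positives respond 10^(0.5 × 0.90) = 2.8-fold or 10^0.90 = 7.9-fold higher. Variance ratios are squared ratios of mean SEs, for example (0.0707/0.0720)² = 0.96.

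| Positive | Slope | Power: titre / growth / adjusted | Titre and growth tests disagree | Adjusted / titre | Adjusted / growth |
|---|---|---|---|---|---|
| 0% | any | about 70% each | 0% | 1.00 | 1.00 |
| 5% | 0 | 68.4 / 61.1 / 68.1% | 13.0% | 1.01 | 0.86 |
| 5% | 0.5 | 68.6 / 66.6 / 69.5% | 12.7% | 0.96 | 0.96 |
| 5% | 1 | 62.2 / 70.5 / 69.7% | 14.3% | 0.86 | 1.01 |
| 10% | 0.5 | 66.3 / 67.1 / 70.3% | 15.6% | 0.93 | 0.93 |

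The Monte Carlo error of each power is √(0.7 × 0.3/2000), about 1 percentage point, so the variance ratios are the steadier guide. Either planned analysis can be the worse one, depending on a slope that is unknown in advance. The adjusted model stays within about 1% of the better.

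**The case against.** The strongest reply is that this is a preference among valid methods. Analysis of variance on log titres of randomised arms is a correct test, covariates are a detail that 10.7.1 may leave to the analysis plan, and the sized comparison is untouched. That stands as to validity. It does not dispose of the point, because the protocol does fix the method and tests both outcomes without ranking them.

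Four stronger readings are tempting, and the documents do not support them.
- *The adjusted model is never less informative.* This is true only in large samples. With an uninformative baseline, its SE exceeded that of the titre analysis in about 78% to 81% of simulated trials, though only by about 0.3%.
- *The plan ignores baseline and age.* Baseline enters growth and the seroconversion definition, and age defines separately randomised cohorts. The text does not say that the analysis of variance is one-way or unadjusted; it only names no covariate.
- *The primary endpoint has two rival answers.* Section 8.7.1 names antibody level, which favours post titre. What is missing is a statement that growth is supportive.
- *The gain is substantial.* Known or suspected COVID-19 cases and RT-PCR positives are excluded (9.3), so most baselines are probably below 1:4, where titre and growth tests nearly coincide.

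Two further limits stand. The simulations cover two arms of 100, so they speak to medium against high dose, not to the three-arm model with placebo, where a common slope is doubtful. And 5% positives means about five subjects per vaccine arm, so the baseline slope would rest on few people. Sex is only implied by the collection of demographic data.

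**Conclusion.** The point holds as a minor improvement, not as the correction of an error. A single adjusted model removes any conflict between titre and growth by algebra, whatever the inputs. It also removes chance imbalance in baseline titre and age.

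The gain in precision is modest and conditional: about 1-4% lower variance from age alone, and about 9-16% against titre and 1-5% against growth with 3-5% baseline-positive subjects. The 9-16% needs the assumed 10-fold higher response. With a 2.8-fold response at 5% positive, the gain from baseline is about 4%. It is near nil if almost all baselines are below 1:4. The price is at most about 2% in variance.

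Residual SD, slopes, GMT ratio and the baseline-positive share are all assumptions; the protocol gives none of them. No stated figure changes.

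**What to change.** In 10.7.4.3, make the between-group test of antibody level one analysis of covariance within each cohort: log post-immunization titre on arm, log baseline titre and age as a continuous term, plus sex if it is recorded. Report the adjusted GMT ratio with its 95% confidence interval. Keep unadjusted GMT and GMI as descriptive figures and say that growth is not tested separately. The handling of baselines below 1:4, and whether placebo shares the slopes of the vaccine arms, can be settled in the analysis plan before unblinding.

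This changes wording only. Baseline titre and age are already collected, and no visit, sample or sample-size figure is affected.
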